### 6.3 Dose Modification /Delays

6.3.1 Dose delays and modifications will be made using the following recommendations. NCI Common Terminology Criteria for Adverse Events (CTCAE) version 4.0 will be utilized for

CONFIDENTIAL

This document is confidential. Do not disclose or use except as authorized.

Version 13.0 Protocol Version Date: 1/09/2015

Toxicity assessments will be done using the CTEP Active Version of the NCI Common Terminology Criteria for Adverse Events (CTCAE) which is identified and located on the CTEP website at: [http://ctep.cancer.gov/protocolDevelopment/electronic\\_applications/ctc.htm](http://ctep.cancer.gov/protocolDevelopment/electronic_applications/ctc.htm).

If possible, symptoms should be managed symptomatically. However, if a seizure occurs, stop medication immediately. Patients will be removed from study, and medical monitor will be contacted. In the case of toxicity, appropriate medical treatment should be used (including antiemetics, anti-diarrheals, etc.).

All adverse events experienced by participants will be collected from the time of the first dose of study treatment, through the study and until the final study visit. Participants continuing to experience toxicity at the off study visit may be contacted for additional assessments until the toxicity has resolved or is deemed irreversible.

If a patient misses study medication for a total of 14 days, they should be discontinued from the study.

Discontinuing or temporally stopping EBRT is at the discretion of the treating physician. Treatment with radiation should be temporarily or permanently stopped due to excessive bowel and/or bladder symptoms not ameliorated with medications or other supportive measures. Temporary stopping the EBRT is not a protocol violation as long as the radiation is completed in nine and half weeks (ten missed weekday treatments during EBRT).

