#### 6.2.2 Management of enzalutamide toxicity

6.2.2.1 If Grade 1–2 toxicities occur, give supportive care per institutional guidelines. No enzalutamide dose reduction should occur. However, at the discretion of the treating physician, an investigator can hold enzalutamide for intolerable Grade 2 toxicity for a maximum of 14 days. Participants should resume enzalutamide at the original dose (160 mg/day). If the participant is not able to resume study medication after being held for 14 days, the participant must be permanently removed from the study.

6.2.2.2 If Grade 3 fatigue occurs, hold enzalutamide and contact the medical monitor for appropriate instructions on dose reduction.

6.2.2.3 If Grade 3 or higher toxicities occur that are considered potentially related to enzalutamide including headache (that interferes with activities of daily living [ADL]), nausea (requiring total parenteral nutrition or intravenous fluids), vomiting (> 6 episodes/24 hours requiring total parenteral nutrition or intravenous fluids), diarrhea (requiring intravenous fluids or hospitalization, or resulting in hemodynamic collapse), or any other toxicity where patient safety is jeopardized, hold enzalutamide. When the toxicity has resolved to ≤ Grade 1, resume study medication at the full dose. Prophylactic medications should be considered as appropriate. If toxicity recurs, hold study medication and adjust or add medications to mitigate the toxicity. When the recurrent toxicity has resolved to ≤ Grade 1, resume enzalutamide at 120 mg/day (3 pills /day). This should be done with the approval of the PI and the medical monitor.

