## 8.0 STUDY CALENDAR

	Screening (4 week period)	Baseline (Day One Cycle 1) 5+/- 3 day	At fiducial placement (3-7 weeks) (Study) (+/- 3 day)	Cycle 2, Day One (+/- 3 day)	Cycle 3, Day One (+/- 3 day)	Cycle 4, Day One (+/- 3 day)	Cycle 5, Day One (+/- 3 day)	Cycle 6, Day One (+/- 3 day)	End of cycle 6 (+/- 3 day)	3  months after completion of cycle 6
Hx/PE	X	X		X	X	X	X	X	X	X
Vital signs	X	X		X	X	X	X	X	X	X
Height/weight 		X		X	X	X	x	x	x	
CBC with diff	X	X		X	X	X	X	X	X	X
Chemistry/LFTs 	X	X		X	X	X	X	X	X	X
Bone Metabolism markers 		X							X	X
PSA	X	X		X	X	X	X	X	X	X
Hormonal measurements 	X 11	X					X		X	
Anthropomorphic measurements  and waist circumference		X							X	
Prostate tissue samples (optional)			X							
Q of L assessment 		X			X		X		X	X
Dispense med/Pill diary		X		X	X	X	X	X	X 7	
Adverse event and con med		X		X	X	X	X	X	X	
EBRT				X 8	X 					
Sign Informed Consent	X									
EKG	X									
Assessment of breast enlargement 		X		*	*	X	*	*	X	

- 1 -bone specific alk phos, serum C-teleopeptide, serum N terminal propeptide of type I collagen (fasting)
- 2- DHEA sulfate, estrogen (estradiol), free testosterone, total testosterone, estrone, androstenedione. These should be done while fasting.
- 3 -Triceps skin fold, biceps (mid-upper arm circumference), shoulder blade and waist. Height will only be necessary at the baseline visit.
- 4- EPIC-26, PROMIS, PSQI
- 5 -Any time between Day -7 to day 1
- 6- +/- 7 days
- 7- Collect pill diary and unused drug
- 8 - EBRT 7-10 weeks after initiating enzalutamide. This could fall on cycle 2 or 3.
- 9 -Chemistries includes: creatinine, BUN, potassium, sodium, bicarbonate LFT's include AST, ALT, total bilirubin and alkaline phosphatase.
- 10- Assessment will be done with calipers. The maximum diameter of the larger breast (if there is asymmetry) at Baseline (Day One Cycle 1), Cycle 4/day 1, End of Cycle 6 and assess it according to these parameters: grade 1 (<=2cm), grade 2 (>2-<=4cm), grade 3 (>4-6cm), and grade 4 (>6cm).
- 11- At screening visit, the only hormonal test required is total testosterone which will not require morning collection or fasting.\* We will ask you to answer a yes or no about breast tenderness and/or enlargement at every study visit.

CONFIDENTIAL

This document is confidential. Do not disclose or use except as authorized.

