#### 9.2.2. Health-Related Quality of Life

HRQoL will be assessed at baseline, at the beginning of cycles 3 day 1, cycle 5 day 1, end of cycle 6 and 3 months after completion of study.

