## 13.2 Analysis of Secondary Endpoints

### 13.2.1 Health related quality of life

The primary HRQoL aim is to assess the change from baseline to the end of cycle 6 in the vitality or hormonal function score as well as the sexuality score on the EPIC-26 questionnaire. It is anticipated approximately 75% of patients will have both scores for each domain. A one-sample t-test will be used to assess the overall change in score. To be considered a clinically meaningful difference will be defined as half historical standard deviation for the specific domain. Given 48 evaluable patients, there is 80% power to detect a 0.41 change in the hormonal domain score of the EPIC-26 assuming 2-sided 5% alpha. Results in this study will be evaluated in the context of past research by Sanda et al showing patients that received radiotherapy with non-hormonal therapy had a score on the vitality or hormonal function domain of approximately 80 and a score on the sexuality domain of 26.

Descriptive statistics at each time point and changes over time will be provided for each of the EPIC-26 domains as well as for the PROMIS-Fatigue and PSQ1. Mixed models will be used to explore the impact of time on quality of life adjusting for prognostic baseline factors.

13.2.2 Safety and Tolerability: We will monitor toxicities experienced by all treated patients. Frequency and severity of worst grade 3 or higher treatment-related AEs by type will be reported along with the incidence of overall grade 3 or higher treatment-related AEs. With 71 treated patients, the maximum width of a 90% CI for a given toxicity is 21%. The probability of observing one rare severe toxicity (true rate=5%) is 97%. Tolerability endpoints include the number of dose reductions and treatment interruptions as well as the number of patients that discontinue treatment due to AEs. The safety summary will include clinical laboratory, ECG and vital signs data.

13.2.3 Hormone Levels: Descriptive statistics at each time point and changes over time will be provided for all hormone measures. Paired t-tests and two-sample t-tests (or non-parametric equivalents) will be used to assess significance of change over 6 cycles of treatment in hormone levels for the overall cohort and by status on primary clinical endpoint (yes or no achieving PSA level  $\leq 0.20$  ng/ml at the end of 6 cycles of treatment with enzalutamide and EBRT).

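### No assessment is scheduled when a man stops enzalutamide early and Section 13.2 has no rule for missing end-of-cycle-6 data, so the HRQoL, hormone and body-composition changes are completer analyses open to selection bias

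*Combined protocol and SAP*

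**What the plan says.** - **Visits.** The Section 8 calendar runs from screening through day 1 of each cycle to the end of cycle 6, then to a visit three months after cycle 6 is completed. It has no column or footnote for early discontinuation. Section 6.3 mentions such a visit once, in its text on adverse events: "Participants continuing to experience toxicity at the off study visit may be contacted for additional assessments". It gives neither timing nor content.
- **HRQoL.** Section 9.2.2: "HRQoL will be assessed at baseline, at the beginning of cycles 3 day 1, cycle 5 day 1, end of cycle 6", and again three months later.
- **Other measures (Section 8).** The full hormone panel is taken at baseline, cycle 5 day 1 and end of cycle 6. Skinfolds and waist are taken at baseline and end of cycle 6 only. Bone markers are taken at baseline, end of cycle 6 and three months later. Breast diameter has one interim measurement, at cycle 4 day 1. Weight is taken at every cycle visit.
- **Leaving the study.** Under Section 6.2.2.1, if drug cannot be resumed after a 14-day hold, "the participant must be permanently removed from the study". Section 6.3 takes men off the study after 14 missed days in total.
- **Staying on study.** Section 5.4.3 lists reasons to end treatment without saying that study visits end. Section 5.5.1 keeps men on study for three months, counted from stopping enzalutamide.
- **Analysis.** Section 13.2.1 tests the change in EPIC-26 from baseline to end of cycle 6 with a one-sample t-test and states: "It is anticipated approximately 75% of patients will have both scores for each domain". Mixed models are planned as an exploratory HRQoL analysis. Sections 13.2.3 and 13.2.4 report change over six cycles for hormones and body measures. Section 13.1 counts early stoppers as failures on the primary endpoint. Section 13.2 has no corresponding rule.

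**The concern.** A change from baseline to end of cycle 6 can be computed only for men who are measured at end of cycle 6. The plan does not require men who stop earlier to be assessed when they stop, and two of its rules take some of them off the study altogether. If those men fared differently on HRQoL or body composition, the reported mean describes a selected group.

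This matters because Section 1.1 expects enzalutamide to compare well with LHRH agonists on these same outcomes and says that convincing data would lead to a randomized phase III trial. Allowing for 25% missing pairs in the sample size protects precision. It does not protect against bias if the missing men differ from the rest.

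**Working it through.** **1. The plan's own figure.** Inputs from Sections 13.1 and 13.2.1: 64 evaluable men, 75% with both scores, two-sided 5% alpha, 80% power, detectable change 0.41.

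- 0.75 × 64 = 48 men with pairs; 64 − 48 = 16 without.
- One-sample t-test at n = 48: power for 0.41 SD is 79.4% (noncentral t) or 81.1% (normal approximation). The effect detectable with 80% power is 0.413 SD (t) or 0.404 SD (normal). The stated figure reproduces, provided 0.41 is read in SD units.
- Power for 0.5 SD is 92.4%.

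**2. What an early stopper contributes under the calendar.**

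| Stops | On-treatment data scheduled | Missing |
|---|---|---|
| Before cycle 3 day 1 | Weight, if a cycle visit was reached | All on-treatment HRQoL, hormones, skinfolds, waist and bone markers |
| From cycle 3 day 1 to before cycle 5 day 1 | One HRQoL score; weight | Hormone panel, skinfolds, waist, bone markers |
| After cycle 5 day 1 | Two HRQoL scores, one hormone panel; weight | Skinfolds, waist, bone markers |

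If Section 5.5.1 keeps a stopper on study, the three-month column would give him HRQoL and bone markers but no hormone panel or skinfolds. Section 2.1.1 puts the half-life at about 6 days, so about 90 days off drug is 90/6 = 15 half-lives. That visit cannot show the on-drug state.

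**3. Possible bias in the HRQoL mean.** Let m be the share of men without an end-of-cycle-6 score because they stopped, and D the amount by which their change is worse than the completers' change, in SD units. If the completers' mean is c, the mean for all men is (1 − m)c + m(c − D) = c − mD. The completers' mean is therefore too favourable by m × D. The documents give neither quantity, so both are assumed.

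| m | D = 0.5 | D = 1.0 |
|---|---|---|
| 0.05 | 0.025 SD | 0.05 SD |
| 8/64 = 0.125 | 0.0625 SD | 0.125 SD |
| 16/64 = 0.25 | 0.125 SD | 0.25 SD |

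**4. Effect on the test.** Take a true worsening of 0.50 SD in all men, the plan's own meaningful difference, and treat the historical SD and the SD of change as equal.

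- Bias 0.025: observed 0.475 SD, power about 90%.
- Bias 0.125: observed 0.375 SD, power about 72%.
- Bias 0.25: observed 0.25 SD, power about 40%.

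Without bias the power is 92%.

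**The case against.** The case on the other side is substantial, and several stronger readings fail against it.

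- **A reader might infer that change is measured only in men who tolerated treatment.** It is not. Under Section 6.2.2, men who resume after a hold, and men who continue at a reduced dose after recurrent Grade 3 or higher toxicity, can reach end of cycle 6.
- **A reader might infer that early stoppers vanish from the tolerability results.** They do not. Section 13.2.2 covers all treated patients and counts dose reductions, interruptions and discontinuations for adverse events. Section 13.1 counts early stoppers as primary-endpoint failures.
- **A reader might infer that no model can recover the lost information.** For HRQoL that is too strong. Scores at cycle 3 and cycle 5 are scheduled, and the planned mixed model can use them. It is closest to true for skinfolds and waist, where an early stopper has no post-baseline value.
- **The Section 6.3 sentence is a weak anchor.** It concerns adverse events and may simply mean the final visit. The calendar and Section 13.2 carry the point.
- **The bias may be small.** The 25% is not attributed to early stopping. In the dose-escalation study in Section 2.1.1, none of 58 patients at 30 to 150 mg/day needed a dose reduction for fatigue, and one of 140 stopped for it, although those men had advanced disease. For serum hormones, nothing in the documents indicates which way missing values would push the result.
- **A late visit would miss the on-drug state.** After a 14-day hold, 14/6 = 2.3 half-lives have passed.

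These points limit the claim and shape the remedy. None supplies the missing assessment or the missing analysis rule.

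**Conclusion.** The gap is real and concerns secondary endpoints; the primary analysis is unaffected. As written, the HRQoL t-test and the six-cycle changes in hormones and body measures are analyses of men measured at end of cycle 6. The gap is clearest for skinfolds, waist and bone markers, and smaller for HRQoL and hormones, which have interim time points.

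The illustrative HRQoL bias is 0.025 to 0.25 SD. The upper end needs all 16 men without pairs to be early stoppers and their change to be a full 1.0 SD worse. At 5% stopping the bias is at most 0.05 SD, small beside 0.41 SD. It would be tempting to conclude that the results are biased in the drug's favour, but the documents do not establish the share of stoppers, the size of the difference or its direction.

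Sections 5.4.3, 5.5.1, 6.2.2.1, 6.3 and the calendar also disagree on whether a man who stops drug remains on study, so how many such men would be assessed later cannot be determined.

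**What to change.** 1. **Section 8:** add an early-discontinuation column with EPIC-26, PROMIS, PSQI, the hormone and bone-marker panel, weight, skinfolds and waist, and breast measurement. Do these as close as possible to the decision to stop enzalutamide, and record days since last dose.
2. **Sections 5.4.3, 5.5.1, 6.2.2.1, 6.3 and the calendar:** reconcile them on whether men who stop drug stay on study for later assessments, and on the date from which the three-month visit is counted.
3. **Section 13.2.1:** estimate the EPIC-26 change from baseline to end of cycle 6 from the planned mixed model, using all available scores, and keep the paired t-test as a sensitivity analysis. Without this step a new column leaves the t-test a completer analysis. The model still assumes that missingness is explained by the scores observed.
4. **Sections 13.2.3 and 13.2.4:** report change to the last post-baseline assessment beside the end-of-cycle-6 result, with the number of missing values and the reasons. The last-value result mixes exposure lengths and should be labelled as such.

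**Cost:** an amendment, and one set of existing questionnaires, measurements and blood tubes for each man who stops early. No extra patients are needed. Section 11.1.2 already requires an off-treatment form within 14 days, and the Schema timeline notes that men who cannot complete enzalutamide still receive EBRT, so many should still be attending clinic. Some values will be taken after partial washout, which is why days since last dose must be recorded.

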## **7.0 CORRELATIVE/SPECIAL STUDIES**

- 7.1 Pharmacokinetics-N/A
- 7.2 Pharmacodynamics-N/A
- 7.3 Assessment of AR localization by IHC. (See section 10.5)

CONFIDENTIAL

This document is confidential. Do not disclose or use except as authorized.

## 8.0 STUDY CALENDAR

	Screening (4 week period)	Baseline (Day One Cycle 1) 5+/- 3 day	At fiducial placement (3-7 weeks) (Study) (+/- 3 day)	Cycle 2, Day One (+/- 3 day)	Cycle 3, Day One (+/- 3 day)	Cycle 4, Day One (+/- 3 day)	Cycle 5, Day One (+/- 3 day)	Cycle 6, Day One (+/- 3 day)	End of cycle 6 (+/- 3 day)	3  months after completion of cycle 6
Hx/PE	X	X		X	X	X	X	X	X	X
Vital signs	X	X		X	X	X	X	X	X	X
Height/weight 		X		X	X	X	x	x	x	
CBC with diff	X	X		X	X	X	X	X	X	X
Chemistry/LFTs 	X	X		X	X	X	X	X	X	X
Bone Metabolism markers 		X							X	X
PSA	X	X		X	X	X	X	X	X	X
Hormonal measurements 	X 11	X					X		X	
Anthropomorphic measurements  and waist circumference		X							X	
Prostate tissue samples (optional)			X							
Q of L assessment 		X			X		X		X	X
Dispense med/Pill diary		X		X	X	X	X	X	X 7	
Adverse event and con med		X		X	X	X	X	X	X	
EBRT				X 8	X 					
Sign Informed Consent	X									
EKG	X									
Assessment of breast enlargement 		X		*	*	X	*	*	X	

- 1 -bone specific alk phos, serum C-teleopeptide, serum N terminal propeptide of type I collagen (fasting)
- 2- DHEA sulfate, estrogen (estradiol), free testosterone, total testosterone, estrone, androstenedione. These should be done while fasting.
- 3 -Triceps skin fold, biceps (mid-upper arm circumference), shoulder blade and waist. Height will only be necessary at the baseline visit.
- 4- EPIC-26, PROMIS, PSQI
- 5 -Any time between Day -7 to day 1
- 6- +/- 7 days
- 7- Collect pill diary and unused drug
- 8 - EBRT 7-10 weeks after initiating enzalutamide. This could fall on cycle 2 or 3.
- 9 -Chemistries includes: creatinine, BUN, potassium, sodium, bicarbonate LFT's include AST, ALT, total bilirubin and alkaline phosphatase.
- 10- Assessment will be done with calipers. The maximum diameter of the larger breast (if there is asymmetry) at Baseline (Day One Cycle 1), Cycle 4/day 1, End of Cycle 6 and assess it according to these parameters: grade 1 (<=2cm), grade 2 (>2-<=4cm), grade 3 (>4-6cm), and grade 4 (>6cm).
- 11- At screening visit, the only hormonal test required is total testosterone which will not require morning collection or fasting.\* We will ask you to answer a yes or no about breast tenderness and/or enlargement at every study visit.

CONFIDENTIAL

This document is confidential. Do not disclose or use except as authorized.

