### 5.2 Agent Administration

5.2.1 Treatment will be administered on an outpatient basis. Expected toxicities and potential risks as well as dose modifications for enzalutamide are described in Section 6 (Expected Toxicities and Dosing Delays/Dose Modification). No investigational or commercial agents or therapies other than those described below may be administered with the intent to treat the participant's malignancy.

CONFIDENTIAL

This document is confidential. Do not disclose or use except as authorized.

Version 13.0 Protocol Version Date: 1/09/2015

5.2.2 Patients will be treated in 6 (28 +/- 3 days) cycles. EBRT will be initiated 7-10 weeks into enzalutamide therapy. Patients will be seen every 28 (+/- 3 days) days for history and physical, adverse event and concomitant medication assessment. At these visits routine laboratory parameters will be obtained and a subset of these must be reviewed prior to dispensing the investigational agent. The routine laboratories at the beginning of each cycle should be completed per the Study Calendar in section 8.

The criteria to treat at the beginning of each cycle are:

- ANC greater than 1,000mm^3
- Hgb greater than 8.0 g/dL
- Platelets greater than or equal to 50,000
- ALT less than 3.5x upper limit normal
- AST less than 3.5x upper limit normal

Any grade (3 or greater) non-hematologic adverse event (such as fatigue, etc.) must be resolved to (grade 1 or less) in order to continue therapy. The Medical Monitor should be notified of any adverse events that require holding, stopping or dose modifications of study drug.

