#### **6.1.3 Enzalutamide**

##### Common

- Peripheral Edema
- Flushing
- Diarrhea
- Neutropenia
- Arthralgia
- Musculoskeletal pain
- Fatigue
- Gynecomastia

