#### 6.2.1.3 Management of gynecomastia

At the discretion of the treating physician, at any time before or during treatment patients are permitted to receive radiation therapy to the breasts to prevent or treat gynecomastia. Treatments such as tamoxifen are not permitted for gynecomastia.

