**Skinfold Testing Technique**

Use your thumb and index finger of your left hand to pinch an area of skin wide enough to get a good fold.

[figure not shown]
Pull out the fold of skin and underlying layer of fat with your left hand away from the body. You do not have to worry about getting any muscle as the muscle is firm and will not come into a fold with the skin and fat.

CONFIDENTIAL

This document is confidential. Do not disclose or use except as authorized.

While holding the skinfold with the left hand, place the jaws of the calipers about 1/4" from the fingers of the left hand. Release the trigger of the caliper so the entire force of the jaws are on the skinfold. Without releasing the skinfold with the left hand, let the force of the caliper creep a bit for a few seconds to settle to the correct reading. Write down the measurement and proceed to the next location.

[figure not shown]

Measurement of lean muscle mass is done by multiplying the weight (in lbs.) by the body fat percentage. See Appendix G.

The breast enlargement assessment will be done with calipers. The maximum diameter of the larger breast (if there is asymmetry) at Baseline (Day One Cycle 1), Cycle 4/day 1, End of Cycle 6 and assess it according to these parameters: grade 1 ( $\leq 2$ cm), grade 2 ( $> 2 - \leq 4$ cm), grade 3 ( $> 4 - 6$ cm), and grade 4 ( $> 6$ cm).

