**Figure 2. Differentiation of Gynecomastia from Pseudogynecomastia and Other Disorders by Physical Examination.**

The patient lies flat on his back with his hands clasped beneath his head. Using the separated thumb and forefinger, the examiner slowly brings the fingers together from either side of the breast. In patients with true gynecomastia, a rubbery or firm mound of tissue that is concentric with the nipple-areolar complex is felt, whereas in patients with pseudogynecomastia, no such disk of tissue is found.

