## **10.4 Reporting to the Study Sponsor 10.4.1**

### **Serious Adverse Event Reporting**

All serious adverse events that occur after the initial dose of study treatment, during treatment, or within 30 days of the last dose of treatment must be reported to the DF/HCC Overall Principal Investigator on the local institutional SAE form. This includes events meeting the criteria outlined in Section 10.1.2, as well as the following:

- Grade 2 (moderate) and Grade 3 (severe) Events – Only events that are unexpected and possibly, probably or definitely related/associated with the intervention.
- All Grade 4 (life-threatening or disabling) Events – Unless expected AND specifically listed in the protocol as not requiring reporting.
- All Grade 5 (fatal) Events – When the participant is enrolled and actively participating in the trial OR when the event occurs within 30 days of the last study intervention.

Note: If the participant is in long term follow up, report the death at the time of continuing review.

Participating investigators must report each serious adverse event to the DF/HCC Overall Principal Investigator as well as the Astellas Safety Department within 24 hours of learning of the occurrence. In the event that the participating investigator does not become aware of the serious adverse event immediately (e.g., participant sought treatment elsewhere), the participating investigator is to report the event within 24 hours after learning of it and document the time of his or her first awareness of the adverse event. Report serious adverse events by telephone, email or facsimile both to:

DF/HCC Overall Principal Investigator and Medical Monitor:

[name]  
[[contact]](mailto:[contact])  
[contact]  
[contact]

Astellas Safety Department:

Astellas Pharma Global Development – United States  
Email: [[contact]](mailto:[contact])  
[contact]

Within the following 24-48 hours, the participating investigator must provide follow-up information on the serious adverse event. Follow-up information should describe whether the event has resolved or continues, if and how the event was treated, and whether the participant will continue or discontinue study participation.

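### The caliper breast-enlargement scale has no zero category, so a man with no palpable disk is coded grade 1 and new growth from 0 to 2 cm shows no change

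*Combined protocol and SAP*

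**What the plan says.** Section 8, footnote 10 sets a caliper assessment of breast enlargement with four steps: "grade 1 (<=2cm), grade 2 (>2-<=4cm), grade 3 (>4-6cm), and grade 4 (>6cm". Section 9.4 repeats the same cut-points ("The breast enlargement assessment will be done with calipers") and fixes what is measured and when: "The maximum diameter of the larger breast (if there is asymmetry) at Baseline (Day One Cycle 1), Cycle 4/day 1, End of Cycle 6". Neither place has a grade 0 or a none-palpable entry, and neither tells sites to leave a man without glandular tissue ungraded.

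The examination technique in Section 9.4 takes the diameter of palpable breast tissue as the objective measure of gynecomastia. The Figure 2 text there separates true gynecomastia, where a disk is felt, from the alternative: "whereas in patients with pseudogynecomastia, no such disk of tissue is found".

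Section 6.1.3 lists "Gynecomastia" among the common effects of enzalutamide. Section 13.2.4 promises descriptive statistics and change over six cycles for anthropomorphic measures in general. It does not name the breast assessment, which is described within Section 9.4 under that title.

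**The concern.** A scale meant to follow a drug effect over time should separate absence from presence. This one does not. A man in whom the examiner feels no disk and a man with a 2 cm disk receive the same grade. Every man is measured at baseline, before exposure, so the scale starts every man at grade 1 or higher, and onset of a small disk on treatment leaves the recorded category where it was.

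The trial argues for enzalutamide partly on its side-effect profile relative to LHRH agonists (Sections 1.1 and 2.3). An effect the protocol itself calls common should therefore be countable from its first appearance. As the scale stands, a table of grade by visit, or of change in grade, would mix men with no gynecomastia and men with small new gynecomastia in a single cell.

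**Working it through.** The plan states no figure on this point, so there is none to reproduce. The check is to apply the scale as written to a range of diameters and see what it records.

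Inputs:
- Cut-points from Section 8 footnote 10, identical in Section 9.4. The third step is read as above 4 cm and up to 6 cm.
- A starting diameter of 0 cm, the no-disk finding in the Figure 2 text of Section 9.4.

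Scale as written, for diameter d in cm: g(d) = 1 if d ≤ 2; 2 if 2 < d ≤ 4; 3 if 4 < d ≤ 6; 4 if d > 6.

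Scale with a zero class: g0(d) = 0 if d = 0, otherwise g(d).

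Change from a 0 cm baseline is g(d) − g(0) = g(d) − 1 as written, and g0(d) − g0(0) = g0(d) with the zero class.

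| Diameter (cm) | Grade as written | Change from 0 cm | Class with zero added | Change from 0 cm |
|---|---|---|---|---|
| 0 | 1 | 0 | 0 | 0 |
| 0.5 | 1 | 0 | 1 | +1 |
| 1 | 1 | 0 | 1 | +1 |
| 1.5 | 1 | 0 | 1 | +1 |
| 2 | 1 | 0 | 1 | +1 |
| 2.1 | 2 | +1 | 2 | +2 |
| 4 | 2 | +1 | 2 | +2 |
| 4.1 | 3 | +2 | 3 | +3 |
| 6 | 3 | +2 | 3 | +3 |
| 6.1 | 4 | +3 | 4 | +4 |

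Three results follow.

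1. The smallest value g can take is 1, so the share of men at grade 1 or higher at baseline is 100% by construction.
2. For a man starting at 0 cm, any new disk of up to and including 2 cm gives a change of 0 as written and +1 with a zero class.
3. A zero class does not capture everything. Growth from 0.5 to 2 cm is class 1 to class 1 under either scale, and only the recorded diameter would show it.

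The documents give no distribution of new disk sizes and no baseline prevalence. The share of new cases that stay at or below 2 cm, and so the understatement of incidence by change in grade, cannot be calculated from them.

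**The case against.** The strongest reply is that the category is not the only record of breast change. The calendar note has men asked at every study visit, yes or no, about breast tenderness or enlargement. EPIC-26 item 13b scores the same pair from 0 to 4, with a true no-problem answer, at baseline, Cycles 3 and 5, the end of Cycle 6 and three months later. Adverse events are collected from the first dose (Section 6.3), with a physical examination at each scheduled visit. The diameter is itself measured, and nothing says the value in cm is thrown away. Finally, no hypothesis, power figure or decision rests on breast grade.

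Most of this stands, and it limits the point. A reader might infer that small new cases go wholly undetected. The documents do not support that: the loss is in the category, not in every record. The other routes are still not equivalent. The yes/no question and item 13b each combine tenderness with enlargement, so a positive answer does not show new tissue, and item 13b rates bother. For adverse events, Section 13.2.2 commits only to summaries of grade 3 or higher treatment-related events, so low-grade gynecomastia need not be tabulated. The diameter would recover onset if kept, but no section says that it is kept or analysed.

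A reader might also infer that a disk above 4 cm sets off the rules for grade 3 and 4 events, because the labels match. Section 5.2.2 says "Any grade (3 or greater) non-hematologic adverse event (such as fatigue, etc.) must be resolved to (grade 1 or less) in order to continue therapy", and Section 10.4.1 lists "All Grade 4 (life-threatening or disabling) Events" for reporting. Both concern adverse events, which Sections 6.3, 9.2.1 and 10.2 grade by CTCAE. No section applies either rule to the centimetre scale. The overlap is one of labels, with at most a risk of misreading.

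**Conclusion.** The point holds for the scale itself. As written, it assigns grade 1 to a man with no palpable disk, places every man at grade 1 or above at baseline, and shows no change for growth from 0 to 2 cm. This follows from the stated cut-points together with the Section 9.4 finding that some men have no disk. It needs no assumption about how many men start without one.

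The consequence is modest. It affects a descriptive safety measure, and the primary endpoint, the sample size and the error rates do not change. Any percentage put on the understatement would only return the assumed share of new disks at or below 2 cm.

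A reader might add the allowance in Section 6.2.1.3 that "patients are permitted to receive radiation therapy to the breasts to prevent or treat gynecomastia" as a further fault of the scale. It has no bearing on the category boundaries, and the documents give no frequency for it, so it forms no part of this conclusion.

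**What to change.** In Section 8 footnote 10 and in Section 9.4:

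- Add class 0, no palpable glandular disk.
- Make class 1 more than 0 and up to 2 cm, and leave the other cut-points unchanged.
- Record the diameter in cm of palpable glandular tissue, as the Section 9.4 technique describes. This also settles what is measured, since footnote 10 speaks of the diameter of the breast.
- In Section 13.2.4, name the breast assessment and report onset (class 0 to class 1 or higher) and change in cm.

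As a minor clarification, call the steps size classes rather than grades, so that they are not mistaken for the CTCAE grades already used for adverse events.

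The cost is a change to one footnote, the matching text in Section 9.4, a line in Section 13.2.4 and one extra field on the case report form. No visit or procedure is added. The drawback is that class 0 cannot be recovered for men already assessed unless their value in cm was kept. Any report should say how many men that affects.
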